If a subject is unwilling to return to the site for evaluation, available information may be collected on the subject's condition via telephone or correspondence. Participation in this study is completely voluntary. If any subject chooses not to participate or removes their consent at any time, subject care must continue according to the physician's standard of care. The site must document changes in subject enrollment via a de-identified summary and forward this information to the sponsor. All subjects who complete the study prematurely will be included in the data analysis up until the time of their study completion.

I. Schedule of Events

Study Activity	Preop	O/D	3 mo (± 2 mo)	1 yr (± 3 mo)	2 yr (± 6 mo)	3 yr (± 1 yr)	5 yr (± 1 yr)	7 yr (± 1 yr)	10 yr (± 1 yr)
Inclusion/exclusion Form	X	-	-	-	-	-	-	-	-
Informed Consent	X	-	-	-	-	-	-	-	-
Demographics/ Med History Form	X	-	-	-	-	-	-	-	-
Clinical KSS/KOOS	X	-	X	X	X	X	X	X	X
Operative/Discharge Form	-	X	-	-	-	-	-	-	-
Radiograph Analysis	-	X	X	X	X	X	X	X	X
Adverse Event Form	-	†	†	†	†	†	†	†	†
End of Study/Exit Form	-	-	†	†	†	†	†	†	†

† This form should be completed when necessary.

VII. DATA COLLECTION

A. Case Report Forms

Case report forms (CRF) will be used to collect the data obtained during this study. Data must be transcribed from source documentation to CRFs. Subject questionnaire data will be recorded directly onto the provided CRFs, and will not be transferred from source documentation.

The CRFs are a set of forms that include questions to record preoperative, operative, discharge, postoperative and x-ray information. A complete set of CRFs will be provided for each subject enrolled.

Smith & Nephew, Inc. currently uses the DataFax data collection system. It allows for case report forms to be faxed directly into the database system. Using this system will increase the speed and efficiency of data collection from the study sites, and will improve the quality of the study data through the use of automated missing data queries. DataFax will also track subject visits according to the scheduled intervals. Periodic due/overdue reports will be sent to the clinical site to help ensure subjects are evaluated at the appropriate intervals.

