Subjects are free to refuse authorization to transfer personal information. If the subject chooses not to agree to this authorization, the subject may be ineligible to participate in the study. If the subject chooses not to sign the authorization, it will not harm relations with the surgeon.

The subject has the right to inspect their medical records at any time. Research records may be unavailable until the conclusion of the study. At that point, it will be made available. The subject may speak with the surgeon in order to access records.

Whenever personal information is processed; it will be kept confidential and secure to the best of the Sponsor and Investigators ability. It will be used only for the purpose for which it was collected.

Retention of Records – The Investigator and Sponsor are required to maintain all study documentation for at least 3-5 years after the conclusion of the study. Thereafter, written permission is required from the study monitor in order to move or destroy any study document. If subjects wish to revoke authorization to use personal information, the subject shall inform their surgeon in writing. Also, even after participation in the study ends, the Investigators and Sponsor may continue to use and disclose the de-identified health information obtained during the study, before the end of study participation.

C. Use of Information and Publication

Should the investigator wish to publish the results of this clinical investigation or the results of the activities in this clinical trial, the manuscript shall be submitted to Smith & Nephew for review prior to submitting the manuscript for publication.

D. Subject Drop-out/Withdrawal

Subjects may withdraw at any point during the study. A final evaluation will be completed for all subjects who do not finish the study, and the reason for the withdrawal will be documented. After withdrawing from the study, no effort will be made to follow the subject. The Investigator will sign an End of Study/Exit case report form stating the reason the subject withdrew from the study. However, some actively enrolled subjects will not return for follow-up exams due to a variety of reasons.

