7.10 Analysis of Primary Endpoint

- Kaplan-Meier product limit survival estimates will be used to estimate implant (device) survivorship, $S(t)$ where $S(t)$ is the proportion of knees without an implant revision at time t . Time to implant revision is the endpoint of interest in the determination of implant survivorship. The cumulative proportion of knees with implant survivorship at 3 months, 12 months (1 year), 24 months (2 years), 36 months (3 years), 60 months (5 years), 84 months (7 years) and 120 months (10 years) will be estimated and displayed accordingly. Knees that are still on-study without a revision will be censored on that date of database lock. A prematurely discontinued knee from study as a result of death or for any other reason will be censored on the discontinuation date. A subject lost to follow-up prior to the database lock will have the contributory knee censored on the last known contact date. Kaplan-Meier estimates for implant survivorship will be presented with the corresponding two-sided 95% Confidence Intervals (CIs). Kaplan-Meier survival graphs will also be displayed.
- A listing of subjects with revised implants and the components revised would be provided.
- The Kaplan-Meier product limit estimates will further be presented after stratifying by age group, BMI group and gender.

CONFIDENTIAL AND PROPRIETARY

This document contains information that is confidential and proprietary to Smith & Nephew PLC and Smith & Nephew, Inc. and is intended for use only by Smith+Nephew and its manufacturer. It shall not be reproduced or copied in whole or in part, nor shall the contents be disclosed by any means without prior written permission from Smith+Nephew, nor shall anyone make any use of it that is contrary to the expressed or implied wishes of Smith+Nephew.

Statistical Analysis Plan

A Prospective, Multi-Center, Non-Randomized, Safety and Efficacy Clinical Study of the LEGION™ Primary Knee System for Primary Total Knee Replacement in Subjects with Degenerative Knee Disease

Number: 10-4042
ST: 1113
Version: Final 1.0, 15-Feb-2021
Page: 16 of 18

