7.15 Changes in Analysis Methods Specified in the Protocol

The protocol-specified analysis of the primary endpoint was planned to be inferentially performed using a non-inferiority approach. This study is now being terminated early, thus, the primary endpoint will only be descriptively summarized.

CONFIDENTIAL AND PROPRIETARY

This document contains information that is confidential and proprietary to Smith & Nephew PLC and Smith & Nephew, Inc. and is intended for use only by Smith+Nephew and its manufacturer. It shall not be reproduced or copied in whole or in part, nor shall the contents be disclosed by any means without prior written permission from Smith+Nephew, nor shall anyone make any use of it that is contrary to the expressed or implied wishes of Smith+Nephew.

Smith+Nephew

Statistical Analysis Plan

A Prospective, Multi-Center, Non-Randomized, Safety and Efficacy Clinical Study of the LEGION™ Primary Knee System for Primary Total Knee Replacement in Subjects with Degenerative Knee Disease

Number: 10-4042
ST: 1113
Version: Final 1.0, 15-Feb-2021
Page: 18 of 18

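### SAP 7.10 carries on-study unrevised knees to database lock without requiring that their revision status be known to that date, so any revision missed after last contact inflates late implant survival

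*SAP*

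**What the plan says.** SAP 7.10 estimates implant survivorship by Kaplan-Meier, with revision as the event, and reports it at seven times from 3 months to 10 years. It has three censoring rules:

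- Active, unrevised: "Knees that are still on-study without a revision will be censored on that date of database lock".
- Lost: "A subject lost to follow-up prior to the database lock will have the contributory knee censored on the last known contact date".
- Discontinued: "A prematurely discontinued knee from study as a result of death or for any other reason will be censored on the discontinuation date".

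SAP 7.15 adds: "This study is now being terminated early, thus, the primary endpoint will only be descriptively summarized".

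Protocol XI.D anticipates silent but active subjects: "However, some actively enrolled subjects will not return for follow-up exams due to a variety of reasons". Protocol VI.I places the last three visits at 5, 7 and 10 years, each with a window of one year either side.

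Several provisions bear on whether revisions become known:

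- Protocol VI.G requires every revision to be recorded.
- Protocol VI.H allows remote contact when a subject will not attend: "available information may be collected on the subject's condition via telephone or correspondence".
- Protocol VII.A and VII.B provide overdue-visit reports and data queries.
- Protocol XI.B and XI.D describe tracing of non-respondents.
- Protocol XI.D adds: "A final evaluation will be completed for all subjects who do not finish the study".
- SAP 7.6 tabulates, by visit, the knees due, expected, not yet overdue and evaluated.

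**The concern.** Carrying a knee to lock treats the absence of a recorded revision as observed revision-free time. That is valid if the database holds every revision up to lock. If an active subject was last contacted at year 7 and revised elsewhere at year 8 without the site hearing of it, the knee stays in the risk set and its event is never counted. The error can only favour the device, and it falls on the late time points. The lost-subject rule avoids this, but the SAP does not say when a silent active subject becomes lost.

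A second gap concerns early termination. A knee active when the sponsor ends the study could be treated as still on study (lock date) or as discontinued for some other reason (discontinuation date). Protocol VI.H says "All subjects who complete the study prematurely will be included in the data analysis up until the time of their study completion". If that covers sponsor-ended subjects, censoring at lock would run past it.

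With the non-inferiority test dropped, the Kaplan-Meier estimate and its interval are the whole primary result.

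**Working it through.** **Inputs from the documents.** Reference survival is 0.95 at 8 years, with a constant hazard (Protocol VIII.A). Visit times and windows are in Protocol VI.I. The plan has 138 enrolled, 96 evaluable and 30% loss by 10 years (Protocol VIII.B).

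**Plan's own figure.** λ = −ln(0.95)/8 = 0.0064 per year, as stated. S(10) = exp(−0.064) = 93.8%, against about 93.7% in the protocol. S(7) = exp(−0.0448) = 95.6%.

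**Assumptions, not in the documents.** Lock falls 8.5–10.5 or 10–11 years after surgery. Attendance per visit is 75% or 90%. Capture is the share of revisions after last contact that are in the database at lock, and is varied from 0 to 100%.

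**Closed form.** Suppose last contact is at 7 years and a share f of all later revisions is missed. Then the estimate at 10 years is exp(−λ[7 + 3(1 − f)]):

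- f = 0: 93.8%, no error.
- f = 0.1: 93.98%, +0.2 points.
- f = 0.5: 94.71%, +0.9 points.
- f = 1: 95.62%, +1.8 points.

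**Simulation.** This used 3 million knees per scenario, with visits uniform within their windows. Overstatement of S(10), in points, by capture:

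| Lock (years) | Attendance | 100% | 90% | 50% | 0% |
|---|---|---|---|---|---|
| 8.5–10.5 | 90% | 0.00 | 0.15 | 0.74 | 1.47 |
| 8.5–10.5 | 75% | 0.02 | 0.20 | 0.90 | 1.77 |
| 10–11 | 90% | 0.00 | 0.08 | 0.39 | 0.77 |
| 10–11 | 75% | 0.00 | 0.11 | 0.54 | 1.08 |

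The 0.02 at full capture is simulation error. At 7 years the overstatement is at most 0.4 points even with no capture. If a final evaluation settles the status of 80% of active knees, the 10-year figures fall to 0.1–0.2 points at 50% capture and 0.2–0.4 at 0%.

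**Scale.** The binomial standard error at 93.8% is √(0.938 × 0.062/96) = 2.5 points with 96 knees and √(0.938 × 0.062/138) = 2.1 points with 138. The 95% interval is therefore about 8 to 10 points wide.

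**Does last-contact censoring remove the error?** A separate simulation used 138 knees, 30% declared lost, and last contact at 7 years for a share of active knees whose later revisions were all missed. The true value was 93.8%.

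| Share of active knees silent | Lock-date rule, mean S(10) |
|---|---|
| 0.1 | 93.9% |
| 0.3 | 94.3% |
| 0.5 | 94.6% |
| 0.8 | 95.2% |

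Ending events and censoring at last contact gave 93.7% to 93.8% throughout.

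**The case against.** The case on the other side has four parts.

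**Capture is not left to chance.** A reader might infer that the study has no means of learning about revisions. The documents do not support that. The reporting duty, remote contact, overdue reports, queries, tracing and final evaluation all work towards capture. Protocol XI.D also asks sites to find out who has become lost, which moves those knees to the last-contact rule. This stands, and it argues against the low-capture figures. However, remote contact is optional, tracing aims at return visits or finding out whether a subject has moved, died or been lost, and none of these steps is tied to lock.

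**The gap would be visible.** SAP 7.6 shows the knees evaluated against those expected, and Protocol VIII.C promises full accountability and an assessment of informative missing data. This stands as disclosure. It does not change the estimate or identify which knees have unknown status.

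**Sponsor-ended knees may already be covered.** Protocol VI.H lists a sponsor decision to end the study among the reasons for removing subjects, and the SAP's discontinuation rule covers any reason. Read together, these suggest censoring at discontinuation, and then most of the modelled error disappears. The reading is natural, but the SAP does not state it. The opposite inference, that these knees are certainly carried to lock, is no better supported.

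**Late follow-up is not mostly unobserved.** A reader might infer that few knees at risk at 10 years were seen near then. With the one-year window, 90% attendance and 30% loss, about 13 of 24 at-risk knees (lock 8.5–10.5 years) or 64 of 95 (lock 10–11 years) would have attended the 10-year visit.

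**Conclusion.** The concern holds in conditional form. The lock-date rule is sound if every revision is captured and biased upward if any after last contact is missed, and the plan does not establish which applies. Under the assumed lock dates and attendance, the 10-year overstatement runs from nil to about 1.8 points. The top of that range needs no capture at all, which the protocol's provisions make unlikely. A larger figure can be produced: about 3.1 points if every active knee was last contacted at year 5 and all later revisions were missed. Nothing in the documents suggests that.

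A reader might also infer that the primary conclusion is unsafe. It is not shown to be: the shift is small against the interval, and SAP 7.15 leaves no formal test for it to affect. The ambiguity over sponsor-ended knees needs no numerical assumption and should be settled in either case. Severity is minor to moderate.

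**What to change.** Amend SAP 7.10 as follows:

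1. State that knees active when the sponsor ends the study are censored at the last date on which revision status is documented, whether by final evaluation, visit, telephone or mail. Use the lock or cut-off date only for knees confirmed revision-free on that date.
2. For unconfirmed knees, end both events and censoring at the last documented contact, and list separately any revision reported later. Cutting only the unrevised knees would create the opposite bias. For example, take 96 knees of which 48 were last contacted at year 7, and one of those 48 is later reported as revised at year 8. With all 96 at risk the drop is 1/96 = 1.0 point. If the other 47 are cut at year 7, it is 1/49 = 2.0 points.
3. Report the lock-date version as a sensitivity analysis, with numbers at risk under both rules.

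The cost is one derived date and a late estimate that is slightly less precise and possibly slightly lower. Some known late revisions would appear in the listing and the sensitivity analysis but not in the main curve. Confirming more knees at cut-off, by contacts the protocol already allows, would reduce both costs.

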7.11 Analysis of Secondary Endpoints

- Surgical and device-related AEs will be summarized using numbers (n) and percentages. The count of episodes for each of these events will also be presented.
- All KSS and KOOS scores will be summarized by visit (preoperative to 10 years) using descriptive statistics for continuous variables. Changes from preoperative to all postoperative visits will additionally be summarized (except for KSS expectation).
- For radiographic evaluations, the proportion of knees with evaluations performed will be summarized. Of those knees with radiographic evaluations performed the proportion of knees with radiolucent lines observed within the femoral zone, tibial ML zone, tibial AP zone and the patellar zone will be summarized. Additionally among knees with radiolucent lines, the number of zones with radiolucent lines present will be summarized using descriptive summary characteristics for continuous variables. The cumulative sum of radiolucent lines will also be summarized using descriptive statistics for continuous variables.
- The proportion of knees evaluated with periosteal hypertrophy, implant loosening, osteolysis or subsidence will be summarized.
- The proportion of knees with patellar problems such as dislocation, abnormal placement or subluxation will be summarized.

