The cumulative percent survival for the study device is unknown for this population, but there is no reason to believe that it would be less than the reference rate. Therefore, a conservative success rate of 93.1% for the study device is used at 10 years. The non-inferiority margin δ of 0.07 is chosen in the study (p13, Chow, Shao, and Wang, 2003). 96 subjects are required to achieve $100(1 - \beta)\% = 80\%$ power to detect non-inferiority at the Significance level of $\alpha = 0.05$. Based on the experience study, allowing 30% of the subjects lost to follow up by the end of 10 years, a sample size of at least 138 subjects are needed in this study. Therefore, a total of 138 subjects will be enrolled into the study in up to 8 clinical sites.

C. Statistical Methods

Primary and secondary outcomes will be evaluated with the use of listings and summary statistics. 95% confidence intervals will be calculated for proportions and averages corresponding to the clinically significant outcomes. Improvement in pain and function will be analyzed using t-test or Wilcoxon Rank tests. Kaplan-Meier estimates will be used to analyze the survivorship of the prosthesis. For survivorship analyses, revision will be defined as failure. Adjustment of prognostic factors to the improvement in outcomes will be performed if needed using appropriate parametric or non-parametric statistical analysis. All statistical analyses and calculation of confidence intervals will be performed using SAS or other appropriate statistical software. An alpha value of $\alpha=0.05$ will be used in all hypothesis testing.

Experience from numerous studies has revealed that most of the missing data are usually due to lost to follow-up, revision, death and subject withdrawal. A complete accountability along with the explanation for lost-to-follow-up, death, revision, and withdrawn subjects will be provided in the final study report. The missing due to revision will be treated as device failure. A complete assessment of the informative/non-informative missing data will be performed using Kaplan-Meier (KM) method. The KM estimate of the success rate along with the 95% confidence interval of the estimate will be included in the final report.

IX. STUDY SUPERVISION

A. Investigator Responsibilities

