4 STUDY OBJECTIVES

The objective of this study is to establish the safety and efficacy of the LEGION™ Primary Total Knee System at each postoperative time point.

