7.2 Analysis Populations

The "Safety" population (SAF) will be used as the analysis population for summarizing all data. This is defined as all knees (or subjects) enrolled into the study and who were implanted with the study device.

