7.13 Analysis of Safety Endpoints

- An overall summary AE table that would summarize as number (n) and percentages (%), the overall incidence according to knees with at least one AE; knees with an AE by worst

CONFIDENTIAL AND PROPRIETARY

This document contains information that is confidential and proprietary to Smith & Nephew PLC and Smith & Nephew, Inc. and is intended for use only by Smith+Nephew and its manufacturer. It shall not be reproduced or copied in whole or in part, nor shall the contents be disclosed by any means without prior written permission from Smith+Nephew, nor shall anyone make any use of it that is contrary to the expressed or implied wishes of Smith+Nephew.

Statistical Analysis Plan

A Prospective, Multi-Center, Non-Randomized, Safety and Efficacy Clinical Study of the LEGION™ Primary Knee System for Primary Total Knee Replacement in Subjects with Degenerative Knee Disease

Number: 10-4042
ST: 1113
Version: Final 1.0, 15-Feb-2021
Page: 17 of 18

relationship to study device; knees with at least one AE with an involvement with a study knee; knees with at least one AE by worst severity (mild, moderate, or severe); knees with at least one AE by worst outcome and; knees with any AE that led to discontinuation from study.

- Other events that will be summarized within the overall summary AE table include SAEs, ADEs, SADEs, UADEs and USADEs. These tables will also include the cumulative episodes of events encountered.
- ISO tables will be summarized as appropriate.
- An AE listing will be provided which would display these AE characteristics by study knee as well as systemic AEs.

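### The adverse event summaries take no account of follow-up time, so with 30% planned loss and early termination the crude percentage will understate the 10-year risk of late device-related events

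*SAP*

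**What the plan says.** Surgical and device-related AEs are a named secondary endpoint (Protocol IV; SAP 5.2). SAP 7.11 gives the method: "Surgical and device-related AEs will be summarized using numbers (n) and percentages". It adds: "The count of episodes for each of these events will also be presented". SAP 7.13 handles the remaining AE classes in the same way ("These tables will also include the cumulative episodes of events encountered"), with an AE listing and ISO tables as appropriate.

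Neither section states a denominator. SAP 7.2 says that the Safety "population (SAF) will be used as the analysis population for summarizing all data", and of that population: "This is defined as all knees (or subjects) enrolled into the study and who were implanted with the study device". No AE section mentions person-time, censoring, cumulative incidence or percentages by follow-up interval.

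Four other statements bear on this:

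- Protocol VIII.B sizes the study "allowing 30% of the subjects lost to follow up by the end of 10 years", and SAP 6.1 repeats the figure. Protocol XI.D says withdrawn subjects are not followed further.
- SAP 7.15 reports: "This study is now being terminated early". The only consequence it draws is for the primary endpoint.
- SAP 4 sets the objective as establishing the "safety and efficacy of the LEGION™ Primary Total Knee System at each postoperative time point".
- SAP 7.10 analyses revision by Kaplan-Meier, with censoring rules and 95% confidence intervals at seven time points from 3 to 120 months.

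**The concern.** Knees will be observed for very different lengths of time. In a percentage over a fixed denominator, a knee last seen at year 1 weighs the same as one seen at year 10, and any event after the last contact is missing from the numerator. Episode counts have the same limitation because no exposure time accompanies them.

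The events most exposed are those that need years to appear. Protocol VI.G counts wear-particle osteolysis, subsidence and migration as device-related AEs. Protocol I.A directs the mid- and long-term radiographs at loosening, osteolysis and migration. These are the events that shortened follow-up hides.

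At stake is how the main safety table reads. It will sit beside a revision curve that does account for censoring, and a reader may take both as 10-year results. The error would favour the device. A single whole-study percentage also does not answer an objective framed by postoperative time point.

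**Working it through.** The documents give no AE rate, so there is no planned AE figure to reproduce. The only sourced input is the 30% loss. It agrees with the plan's own enrolment figure: 96 / (1 − 0.30) = 137.1, rounded up to 138.

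**Inputs**

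- Loss: 30% by 10 years (Protocol VIII.B; SAP 6.1). Taken as exponential and independent of events, g = −ln(0.70)/10 = 0.03567 per year. The exponential form and independence are assumptions.
- True 10-year risk: 10%, assumed. At constant hazard, h = −ln(0.90)/10 = 0.01054 per year.
- Cut-off from early termination: assumed uniform over a two-year range. The documents give no enrolment dates or distribution of follow-up at termination.
- Death is not modelled separately.

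**Formula.** For a knee with administrative limit T, the chance that an event is observed is

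crude(T) = h/(h+g) × [1 − exp(−(h+g)T)], with h+g = 0.04620 and h/(h+g) = 0.2280.

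**Loss alone (T = 10).** exp(−0.4620) = 0.90 × 0.70 = 0.63, so crude = 0.2280 × 0.37 = 0.0844. The 10% risk appears as 8.4%, a ratio of 0.84.

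**Loss plus cut-off at 8 to 10 years.** The mean of exp(−(h+g)T) over that range is 0.660, so crude = 0.2280 × 0.340 = 0.0775. It appears as 7.8%, a ratio of 0.78.

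**Other assumed cut-offs and a rising hazard** (Weibull shape 2, same 10% risk, by numerical integration):

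| Follow-up | Constant hazard | Rising hazard |
|---|---|---|
| 30% loss only | 8.4% | 7.9% |
| plus cut-off 8–10 y | 7.8% | 6.6% |
| plus cut-off 7–9 y | 7.0% | 5.4% |
| plus cut-off 6–8 y | 6.3% | 4.3% |
| plus cut-off 5–7 y | 5.5% | 3.3% |

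At constant hazard the ratios hardly move with the assumed risk. For a true risk of 20% they run from 0.85 to 0.56 over the same rows.

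**Perioperative events.** Take an assumed 5% risk confined to the first 90 days (0.25 year): h = −ln(0.95)/0.25 = 0.2052, and crude = 0.2052/0.2408 × [1 − exp(−0.2408 × 0.25)] = 0.0498. The ratio is 0.996, a shortfall of under 1%.

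**Exposure-adjusted rate.** With loss alone, expected time observed is 0.37/0.04620 = 8.01 years per knee. The rate is 0.0844/8.01 = 1.05 per 100 knee-years, which equals h. It stays at 1.05 under every cut-off in the constant-hazard column.

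**The case against.** The strongest reply is that the SAP claims less than a critic might suppose. It never calls the AE percentage a 10-year risk, and SAP 7.13 presents its table as overall incidence. A count and percentage of events seen is a legitimate description. That stands: the shortfall arises only when the figure is read as a risk over a fixed horizon.

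A reader might go further and infer that the AEs are reported only as crude percentages of all implanted knees, so that AE risk in general is understated. The documents do not support this:

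- Episode counts, ISO tables and an AE listing are also planned, although none uses exposure.
- SAP 7.11 does not name implanted knees as the denominator. That is inferred from SAP 7.2, which leaves knees or subjects open.
- Surgical events are likely to be mainly perioperative, when nearly every knee is under observation.

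Some late events are also covered elsewhere. SAP 7.11 summarises loosening, osteolysis and subsidence as proportions of knees evaluated, events leading to revision enter the Kaplan-Meier analysis, and SAP 7.6 tabulates attrition. This softens the concern without removing it. Migration is not among those radiographic proportions, no visit schedule is stated for them, and SAP 7.6 is not tied to AE denominators.

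Finally, no hypothesis or threshold depends on AEs, and the primary analysis is itself now descriptive. That limits the consequence to how the safety results are read.

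**Conclusion.** The concern holds for late device-related AEs and should be addressed. No planned AE summary reflects follow-up time, although loss is expected, follow-up stops at withdrawal, the study ends early, and the same SAP handles censoring for revision.

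Under the stated assumptions, a 10% true 10-year risk loses about 16% of its value to the planned loss alone and about 22% with an 8 to 10 year cut-off, at constant hazard. The shortfall grows with earlier cut-offs or a rising hazard. These are illustrations and not estimates for this study: the 30% is a planning figure, and every other input is assumed. They also rest on independent loss and leave death out; where death ends follow-up, the attainable cumulative incidence is lower and the gap narrower. The downward direction is secure for any event that can arise after some knees have left observation, if leaving is unrelated to the event. No material understatement is shown for perioperative events.

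**What to change.** In SAP 7.11, with a matching line in 7.13:

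1. Keep n (%) and episode counts. State the denominator for each table, knees or subjects; SAP 7.5 records bilateral status, so the two may differ.
2. Add device-related AE rates per 100 knee-years.
3. Add cumulative incidence of first device-related AE, with 95% confidence intervals and numbers at risk, at the SAP 7.10 time points (3, 12, 24, 36, 60, 84 and 120 months, as far as follow-up reaches).
4. Treat death as a competing event, and revision too where it precludes the AE. Censor event-free knees at last contact or assessment. The SAP 7.10 rules should not be carried over unchanged: they censor deaths, which would push cumulative incidence upward, and they censor on-study knees at database lock, which may credit time with no assessment.

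The cost is modest programming, no new visits, and slightly less favourable AE figures. One check is needed first. Protocol VI.G explicitly requires onset dates for serious events and deaths, so the sponsor should confirm that the case report form records them for non-serious device-related AEs. If it does not, use the visit of first report and say so.
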